Cow milk allergy (CMA) and egg allergies are the most common food allergies in children and recent reports suggest that rates of resolution are considerably lower than previous estimates.⁽¹⁵⁻¹⁷⁾ Further, both CMA and egg allergy are associated with severe anaphylaxis^(18;19) and due their ubiquitous use in our diet are almost impossible to strictly avoid.⁽²⁰⁻²²⁾ In line with these, several studies suggest that quality of life of patients with milk/egg allergy and their families is severely impaired.⁽²³⁻²⁵⁾

With the support of AllerGen NCE and CIHR we have initiated in 2014 the first cross Canada study to assess milk desensitization. This study now includes almost 50 patients,

and our preliminary results reveal an almost 80% success rate . We are now proposing to initiate an egg desensitization study based on the expertises, recruitment skills and data collected in our first 2 years of milk desensitization.

We hypothesize that there will be at least 50% improvement in the ability to tolerate egg. E.g. a child that was able to tolerate only 40 mg of merengue will be able to tolerate at least 60 mg subsequent to desensitization

The trial design is an RCT aiming to demonstrate superiority of the desensitization protocol to an avoidance strategy regarding the tolerated quantity of egg . The ratio of patients to control is 1:1 . Patients will be block randomized in groups of 2 according to age and sex.

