Desensitization will begin with combined challenge/rush desensitization. After placement of an intravenous catheter, 20 ml blood samples will be collected, skin prick test (SPT) to egg will be performed and 5 ml of saliva will be collected. These samples will be used to establish participants' baselines for the various biological markers being examined during the study. The modified challenge will begin with a first single dose of 0.1 mg of placebo, alternating with powdered egg white in the form of Meringue powder. After the initial dose, subjects will receive approximately doubling doses every 30 minutes until the highest tolerated single dose will be determined (see Appendix B for Challenge/Rush doses). For doses of 25 mg and greater, powdered meringue will be dispensed from individual preweighed containers.. After the initial dose, subjects will receive approximately doubling doses every 30 minutes until the highest tolerated single dose was determined. All doses will be mixed with an acceptable vehicle food chosen by the subject and his or her parent. Subjects treated for reactions will be observed for 2 hours, and if there is no evidence of an allergic reaction, they will be discharged home. Self-administered epinephrine will be provided to all patients' caregivers, along with instructions and indications for administration and education about the nature of possible reactions to OIT. To ensure there were no ill effects of the daily dosing, each subject will return to the CIM on the second day for an observed administration of the starting daily dose.

All challenges and escalation doses will take place in the Center of Innovative medicine (CIM) as is currently done for our milk and peanut desensitization study . The CIM services include equipment and medications required to monitor and treat potential reactions . The CIM nurse that will assist in the desensitization protocol is a nurse that has been trained to work in an intensive care unit. The patients will not be admitted, but will remain under observation for 7 h each day, with the possibility for increasing this period if required.

SPT with the allergens listed above will be performed on all patients before starting desensitization, and the tests will be repeated at 3, 6 and 12 months. Blood tests will be also performed to measure sIgE and sIgG, T cell phenotypes (including regulatory Tcells), salivary IgA and DNA methylation before desensitization, at 3 weeks and at 3, 6 and 12 months.

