The patients' parents will be instructed verbally and in writing about the recommendations to be followed after desensitization and how to treat possible allergic reactions. They will also given a direct telephone line for consultation. Patients will be instructed not to perform physical exercise ^(70;71) for 2 h after eating egg and not to take non-steroidal anti-inflammatory drugs for 3 h before or after ingestion. No special recommendations will be given for viral infections.⁽¹¹⁾ Participants will be given

symptom diaries and instructed to complete it daily to keep track of their allergic symptoms during the desensitization process.

Participants who are not able to achieve desensitization (desensitization defined as being able to tolerate the 300 mg maintenance dose) by 18 months following the initiation of the desensitization process will be considered treatment failures and discontinued from the study.

Maintenance/ Follow-up Phase

Once subjects reached the daily dose of 300 mg, they will be instructed to take this daily for the length of the study (12 months). The subjects will be also instructed to otherwise continue an egg-elimination diet for the duration of the study. Subjects and families will be asked to complete daily home diaries to document that daily doses were taken, as well as to report accidental ingestions, problems with dose administration, or related symptoms. Follow-up visits in addition to and in conjunction with the biweekly visits for dose escalation will be planned at 3, 6, 9, 12 months from the second egg challenge. Each visit will involve a medical history and physical examination. egg specific skin prick testing (SPT), a blood draw similar to that at the challenge to measure serum egg-specific IgE and IgG concentrations, T cell penotyping and DNA methylation. A 5 ml saliva sample will be collected to assess salivary IgA

Food challenges

One month after subjects reach the 300 mg dose, they will undergo a second food challenge to determine his or her allergenic reactivity to egg protein. Subjects will continue OIT dosing through the day before the challenge. The challenge will consist of 10 doses of powdered egg white given every 10 to 20 minutes in increasing amounts up to a total of 8 g of powdered egg white (6 g of egg protein).

After their year in the control arm, , oral desensitization will be offered to the control patients

Variables measured. The following variables will be measured in each patient:

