Appendix B. protocols.

Initial Egg Challenge/Desensitization doses ^{(12)*}:

Dose (n:0)	Mg egg protein	Dosage form
1	0.1	Excipient microcrystalline cellulose
2	0.2	” — —
3	0.4	” — —
4	0.8	” — —
5	1.5	” — —
6	3	” — —
7	6	” — —
8	12	Dose of the powder
9	25	” — —
10	50	” — —
11	75	” — —
12	100	” — —
13	125	” — —
14	150	” — —
15	200	” — —
16	250	” — —

17	300	” —
-----------	------------	----------------

Increasing doses are given approximately every 30 minutes. If the subject does not tolerate a given dose and symptoms are mild, then that dose or the previously tolerated one is repeated, and the protocol proceeds as outlined. If the subject experiences significant symptoms, then the protocol is stopped, and the highest tolerated dose is used as the starting daily dose.

Post – Escalation Egg challenge (Egg Protein):

Number of dose	Egg protein mg at each challenge dose	Cumulative dose
1	1mg	1
2	3mg	4
3	10mg	14
4	30mg	44
5	100mg	144
6	300mg	443
7	600mg	1043
8	1000mg	2043
9	2000mg	4043
10	2000mg	6043

10 doses of powdered Meringue given every 10 to 20 minutes in increasing amounts up to a total of 10 g of powdered egg white (6.04 g of egg protein which is equivalent to 1 egg).

Scale for Grading Reaction Severity and management

Score	Symptom	Action
Mild	Pruritus, Urticaria, Flushing, Rhinoconjunctivitis	Observe May give Antihistamine (e.g. Benadryl or Reactin as prescribed) Call Research Team Research team will evaluate if dose adjustment is needed and if next dose will be given at home or in hospital.
Moderate	Angioedema, Throat tightness, Gastrointestinal complaints (cramping, pain, vomiting, diarrhea) Respiratory symptoms (Cough, Mucous production)	Give epinephrine IM as per protocol Give Antihistamine (e.g. Benadryl or Reactin as prescribed) Seek urgent care (hospital emergency room) Call Research team To give next adjusted dose in hospital research unit (CIM)
Severe	Wheeze, Respiratory Distress Hypoxia, Cyanosis, Hypotension Circulatory collapse (Shock)	Give epinephrine IM as per protocol Give Antihistamine (e.g. Benadryl or Reactin as prescribed) Call 911 Seek urgent care (transfer to hospital emergency room) Call Research team; if the symptoms are not improving within 10 minutes of the first dose, instructions will be given from the team regarding use of a second dose of epinephrine.

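### The challenges before and after treatment differ in dose ladder, spacing and ceiling and share no scoring rule, so a 50% gain in tolerated egg can arise partly from the change of instrument

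*Combined protocol and SAP*

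**What the plan says.** **Aim and test.** Section 3.ii hypothesises a gain of half or more in the egg a child can take, for example "a child that was able to tolerate only 40 mg of merengue will be able to tolerate at least 60 mg", and sets superiority in tolerated quantity as the trial's aim. Section 5 bases 17 children per arm on that 50% and names paired t-tests. Neither section says whether the quantity is a single or a cumulative dose.

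**Day-1 challenge.** Section 4, Desensitization to egg: "subjects will receive approximately doubling doses every 30 minutes until the highest tolerated single dose will be determined". The Appendix B table headed "Initial Egg Challenge/Desensitization doses" lists 17 doses from 0.1 to 300 mg egg protein, with "Increasing doses are given approximately every 30 minutes" below it. It has no cumulative column.

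**Second challenge.** Section 4, Food challenges, places it one month after a child reaches 300 mg daily. Appendix B has "10 doses of powdered Meringue given every 10 to 20 minutes in increasing amounts". Its table gives "Egg protein mg at each challenge dose" (1 to 2000 mg) beside a cumulative dose ending at 6043 mg. No scoring rule is given.

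**Amount of powder.** Section 4 has "up to a total of 8 g of powdered egg white (6 g of egg protein"; Appendix B has "up to a total of 10 g of powdered egg white (6.04 g of egg protein which is equivalent to 1 egg".

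**Outcomes and entry.** The primary variable is a one-year status in three categories, with boundaries at 30 and 300 mg. A secondary variable, the lowest dose causing symptoms, draws on both the desensitization protocol and the challenges. Under the inclusion criteria, a positive oral challenge is only one of three alternative confirmatory tests.

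**The concern.** A paired before-and-after comparison assumes that both readings come from the same scale. These two readings differ in number of steps, step size, spacing and highest recordable value, and only the first has a stated metric. They are nevertheless the only challenges described that could supply the pair.

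Because entry does not require a positive challenge, a child may complete the day-1 ladder without reacting. That child's baseline is then unknown above 300 mg, while the second challenge can record up to 2000 mg. Any tolerance between those values that was present from the start would be counted as a treatment gain. The open choice between single and cumulative dose adds a second way for the result to depend on scoring.

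**Working it through.** **Inputs (Appendix B, mg egg protein)**
- Day 1: 0.1, 0.2, 0.4, 0.8, 1.5, 3, 6, 12, 25, 50, 75, 100, 125, 150, 200, 250, 300.
- Second challenge: 1, 3, 10, 30, 100, 300, 600, 1000, 2000, 2000.

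**Step 1. Reproduce the plan's cumulative column.** 1 + 3 + 10 + 30 + 100 = 144; 144 + 300 = 444 (printed 443). The sums then run 1044, 2044, 4044 and 6044 (printed 6043). The column reproduces apart from a 1 mg slip that starts at dose 6 and carries down.

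**Step 2. Day-1 running sum (not in the plan).** The first eight doses sum to 24. The sum then runs 49, 99, 174, 274, 399, 549 (at 150 mg), 749 (at 200 mg), 999 and 1299 (at 300 mg). Reaching the same 300 mg step therefore takes 1299 mg in total on day 1 and 444 mg later, a ratio of 1299/444 = 2.9.

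**Step 3. Ceiling effect, single dose at both challenges.** Change = later/baseline - 1. For a child recorded at 300 mg on day 1, the later score can be 600 mg (+100%), 1000 mg (+233%) or 2000 mg (2000/300 - 1 = +567%) with no true change. In raw mg the largest artefact is 2000 - 300 = 1700 mg. If all 17 treated children had both challenges, one such child would move the mean change by 1700/17 = 100 mg.

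**Step 4. Mixed metrics.** Baseline single 300 mg against later cumulative 444 mg at the same step: 444/300 - 1 = +48% (443 gives the same rounded figure).

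**Step 5. Cumulative dose at both challenges.** A change from 200 to 300 mg single is 300/200 - 1 = +50%, exactly the hypothesised effect. Cumulatively it is 444/749 - 1 = -41%. For 150 to 300 mg the figures are +100% and 444/549 - 1 = -19%. Over all 17 x 10 = 170 pairings of last tolerated steps, the sign reverses in 7. Restricted to a later single dose of at least 300 mg (17 x 5 = 85 pairings), it reverses in 4, all with a day-1 dose of 150 mg or more. In 6 of those 85, the two metrics disagree on whether 50% was reached. These are counts of pairings, not of children.

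**Step 6. Resolution.** Successive doses on the second ladder differ by ratios of 3.0 to 3.3 up to 300 mg, then 2.0, 1.67 and 2.0 (the last dose repeats 2000 mg). The smallest real step, 600 to 1000 mg, is +67%, so a 50% gain is finer than any step. Take a child who tolerates 200 and reacts at 250 mg on day 1, then tolerates 300 and reacts at 600 mg. The threshold ratio lies between 300/250 = 1.2 and 600/200 = 3.0, a gain of anywhere from 20% to 200%.

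**The case against.** The strongest reply is that the metric is less open than it looks. Day 1 is explicitly a single dose, the second table has its own single-dose column, and treatment failure is defined against the single 300 mg maintenance dose. Comparing single with single is the natural reading. That stands, and it makes the mixed comparison a risk of loose wording, not something the plan prescribes. It does not remove the ceiling effect, which arises with single doses at both ends.

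The ladders also serve different purposes: day 1 doubles as rush desensitization and sets the home dose, while the second tests reactivity up to about one egg. That explains the difference but does not make the readings comparable.

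Three stronger readings are tempting and are not supported:
- **That the direction of change generally reverses.** It needs a day-1 cumulative total that the plan neither tabulates nor uses, and few pairings show it. A child going from 25 to 300 mg improves on both metrics (+1100% single; 444/49 - 1 = +806% cumulative).
- **That the plan's 40-to-60 mg example would be mis-scored by a known amount.** The example is in mg of meringue and the ladders are in mg protein, and the documents give two conversions (6/8 and 6.04/10). A child limited to 60 mg would also not normally reach the second challenge. The same applies to a child unchanged at 100 mg.
- **That the primary variable is an artefact of the ladders.** It is a status at one year, not a change between these two challenges.

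**Conclusion.** The point holds for the 50% hypothesis and the paired t-test, and it touches the secondary variable on lowest triggering dose because that pools both ladders. The main defect is the unequal ceiling with no censoring rule: up to +567% for a child who completes the day-1 ladder. The unstated metric is second: about +48% with no change of step if metrics are mixed, and a possible sign reversal for high day-1 thresholds if cumulative doses are compared.

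This rests on two assumptions. The first is that the paired quantity comes from these two challenges, which the plan implies but does not state. The second is that some children reach 300 mg on day 1. The entry criteria permit this, but the documents give no distribution of baseline thresholds, so the number affected cannot be estimated.

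**What to change.** Change the scoring and analysis text only; the challenge doses are not addressed here.

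1. Define tolerated quantity at both challenges as the highest single dose, in mg egg protein, taken without a reaction. Do not compare cumulative doses across the ladders.
2. Record completion of the day-1 ladder as at least 300 mg (right-censored). By the same logic, record completion of the second as at least 2000 mg.
3. Record the last tolerated and first reacting dose, and analyse change with thresholds as intervals between them instead of a paired t-test on raw mg. Collapsing both ladders onto shared steps (3, 100 and 300 mg) is a poor substitute: it drops the primary variable's 30 mg boundary and pools everything from 300 mg up.
4. Restate the 50% criterion in mg protein at a size these ladders can resolve.
5. The sponsor must reconcile the 8 g and 10 g powder figures, and should correct the 443/444 slip.

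The cost is some wording, two form fields per challenge and a slightly more complex analysis. One limit remains: at the 300 mg step a child has already taken 1299 - 300 = 999 mg on day 1 but 444 - 300 = 144 mg at the second challenge, at different spacing. Single-dose scoring therefore does not make the two challenges identical, and the report should say so.

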Reactions during the desensitization protocol will be classified according to the categories proposed by Perry et al.⁽⁶⁹⁾: mild reactions are defined when symptoms are limited to the oral mucosa or the skin; severe reactions include cardiovascular or respiratory symptoms or involvement of any four systems; all other reactions will be classified as moderate, although we will consider isolated abdominal discomfort as mild when it lasted for 30 min or less (appendix C protocols).

Build-up phase

Subjects will begin daily home dosing based on the highest dose tolerated during the modified rush of powdered egg white in 1 to 2 tablespoons of baby food or other acceptable vehicle food. Home doses will be provided in individual pre-weighed containers, and subjects will be instructed to ingest 1 dose daily for 2 weeks. As long as

subjects tolerate current doses, the doses will be increased every 2 weeks (see dosing schedule Appendix B) until reaching 150 mg and then increased by 50 mg at each visit until reaching maintenance (300 mg). Dose escalations will be made at visits in the research unit to ensure that subjects tolerate increases, and subjects will be observed for at least 2 hours after increases for signs of clinical reactions. Subjects will be given diaries to track their dose-related symptoms during the study

The protocol will be individualized according to each patient's tolerance to egg:

- Mild allergic reactions will be treated when necessary and the regimen will be continued when the patient becomes asymptomatic. The previously tolerated dose will be repeated before resuming the process.

- Moderate reactions will be treated and desensitization would be restarted on the following day at the previously tolerated dose.

- Severe reactions will be treated with the necessary measures and in the appropriate department, followed by an assessment of whether to interrupt desensitization or reduce the dose on the following day to 1/10 of the dose that caused the reaction.

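### Section 4 and Appendix B grade cough and brief abdominal discomfort differently, with overlapping reach in home dosing, and give two powder totals for the same egg challenge

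*Combined protocol and SAP*

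**What the plan says.** **Grading in section 4.** Just before the Build-up phase, the protocol adopts a cited published classification for reactions that occur under the desensitization protocol. It says that "severe reactions include cardiovascular or respiratory symptoms or involvement of any four systems". It adds its own rule that isolated abdominal discomfort is mild if it lasts no more than 30 minutes. The Build-up phase, which opens with daily dosing at home, then ties handling to grade. After a mild reaction, treatment is given if needed and the regimen goes on once symptoms clear. After a severe one, the team considers interrupting or cutting the next day's dose to a tenth.

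**Grading in Appendix B.** The severity and management table lists as moderate "Angioedema, Throat tightness, Gastrointestinal complaints (cramping, pain, vomiting, diarrhea" and also "Respiratory symptoms (Cough, Mucous production". The actions in that row include "Give epinephrine IM as per protocol", "Seek urgent care (hospital emergency room" and "To give next adjusted dose in hospital research unit (CIM". The table states no phase or setting.

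**Outcome.** In Variables measured, secondary variable 1 is the number and severity of adverse reactions in the desensitization and follow-up phases. It names no scale.

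**Challenge.** Under Food challenges, section 4 describes ten doses, 10 to 20 minutes apart, totalling 8 g of powdered egg white or 6 g of protein. Appendix B describes the post-escalation challenge with the same number of doses and the same spacing, totalling 10 g of powder or 6.04 g of protein.

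**The concern.** Both texts set out to grade reactions and to say what follows from the grade, yet they disagree on symptoms that each covers. If both apply to the same event, staff and families of children aged 6 to 18 hold two instructions. For brief abdominal discomfort, one of them includes epinephrine and a visit to an emergency room. The same event could also be counted under two severities in secondary variable 1.

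The challenge raises a different problem. Its doses are tabulated in mg of protein but given as powder, so each must be converted to a powder weight, and the documents imply two conversions. Secondary variable 2, the lowest dose that triggers symptoms in a desensitization or challenge session, is affected if its unit is not clear.

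**Working it through.** **1. The two scales side by side**

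| Event | Section 4 | Appendix B table |
|---|---|---|
| Cough | Severe, as a respiratory symptom with no exception | Moderate, named under respiratory symptoms |
| Isolated abdominal discomfort, 30 minutes or less | Mild | Moderate by the natural reading (cramping and pain are listed, with no duration limit) |
| Handling of cough | Necessary measures, then interruption or a tenth of the dose is considered | Epinephrine, antihistamine, urgent care, call to the team, adjusted next dose in the research unit |
| Handling of brief abdominal discomfort | Treatment if needed, regimen continues | The same moderate-row actions, including epinephrine and urgent care |

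The grade conflict for cough is direct, because both texts speak of respiratory symptoms. The clear handling conflict is the last row.

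**2. Reach of each scale**

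- Section 4's classification covers the desensitization protocol. Subject Recruitment and Retention places that protocol at the research centre under staff supervision.
- Appendix B states no scope. Its calls to the team and to 911 read like instructions for caregivers.
- Section 4's handling rules nevertheless stand under the Build-up phase, where doses are taken daily at home. Both texts can therefore apply to a reaction at home.
- Secondary variable 1 includes follow-up. Section 4 supplies a classification for desensitization only.

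**3. Challenge totals**

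Inputs: the ten doses and 10 g of powder from Appendix B; 8 g of powder and 6 g of protein from section 4.

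- Protein: 1 + 3 + 10 + 30 + 100 + 300 + 600 + 1000 + 2000 + 2000 = 6044 mg. The table prints 6043 because dose 6 shows 443 where 144 + 300 = 444. This 1 mg slip is trivial. The stated 6.04 g is reproduced and agrees with the rounded 6 g.
- Powder: 10 / 8 = 1.25, a gap of 2 g.
- Implied protein content: 6 / 8 = 0.750; 6.04 / 10 = 0.604.
- Ratio of the two conversions: 0.750 / 0.604 = 1.24.
- Example, dose 6 (300 mg protein): 300 / 0.750 = 400 mg of powder; 300 / 0.604 = 497 mg.

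Rounding to whole grams does not close the gap: 8 g could be at most 8.5 g and 10 g at least 9.5 g.

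**The case against.** The best defence is that the scales serve different settings: section 4 for supervised dosing, Appendix B for caregivers. Section 4 does limit its own scale, and the location statement and the 911 instruction fit this reading. A reader might infer that neither scale has any stated scope; that goes too far. The split is nonetheless never stated, and the home-dosing overlap remains.

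For cough, the handlings may be compatible. A tenth of the dose is an adjusted dose, and section 4's necessary measures do not exclude those that Appendix B lists. A reader might infer two irreconcilable instructions for cough; the text firmly supports only a conflict of grade.

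Appendix B does not use the term abdominal discomfort, so placing it among gastrointestinal complaints is an inference, though the natural one.

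A reader might also set "mild reactions are defined when symptoms are limited to the oral mucosa or the skin" against Appendix B's mild row, "Pruritus, Urticaria, Flushing, Rhinoconjunctivitis", and conclude that rhinoconjunctivitis changes grade, or that angioedema confined to skin or mouth does. Section 4 names neither, and the classification it cites is not reproduced in the documents. Neither is relied on here.

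On the powder, two products could differ in protein content. The documents do not say this. Section 4 describes powdered egg white in meringue form, and Appendix B uses both names in one sentence.

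**Conclusion.** The plan contradicts itself as written on two separate matters.

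1. Cough changes grade between section 4 and Appendix B. Brief isolated abdominal discomfort changes grade and handling, provided that it counts as a gastrointestinal complaint in Appendix B. The overlap is firm for home dosing in build-up. Desensitization has a designated classification, which Appendix B contradicts without reconciliation; follow-up has none. The number of reactions affected cannot be derived from the documents.
2. For the same challenge, the protein totals agree and the powder totals do not: 8 g against 10 g, or a factor of 1.24 in powder for a given protein dose.

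A reader might infer that the grading conflict reaches the primary variable. It does not: that variable is defined by the amount of egg tolerated and uses no severity grade. A reader might also assume that events could simply be regraded from the diaries. The diaries record symptoms, but nothing says that they record duration, which the 30-minute rule needs.

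Two points are minor. Section 4's classification refers to protocols in Appendix C, which is now the budget. The 30 mg and 300 mg cut-offs of the primary variable do not say whether they mean powder or protein.

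**What to change.** - Reconcile the two grading texts and their linked actions, or state the setting and phase in which each applies, with home dosing covered explicitly.
- Name one scale for secondary variable 1 in both desensitization and follow-up, and fix it before events are analysed. Make sure that the record captures what this scale needs, including symptom duration if a duration rule is kept.
- Reconcile the 8 g and 10 g totals to one powder-to-protein conversion.
- Minor: correct the appendix pointer in section 4, and state the unit of the 30 mg and 300 mg cut-offs.

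Which grade, action, amount or unit is right is for the investigators to decide. The cost is protocol wording, plus a duration entry in the record if one is needed and not already there. No extra visits or patients are required.
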